11.2.4 Compliance with Trial Registration and Results Posting Requirements

Under the terms of the Food and Drug Administration Modernization Act (FDAMA) and the Food and Drug Administration Amendments Act (FDAAA), the Sponsor-Investigator of the trial is solely responsible for determining whether the trial and its results are subject to the requirements for submission to <http://www.clinicaltrials.gov>. Information posted will allow subjects to identify potentially appropriate trials for their disease conditions and pursue participation by calling a central contact number for further information on appropriate trial locations and trial site contact information.

11.2.5 Record Retention

Essential documents are those documents that individually and collectively permit evaluation of the study and quality of the data produced. After completion of the study, all documents and data relating to the study will be kept in an orderly manner by the Investigator in a secure study file. Essential documents should be retained for 2 years after the final marketing approval in an ICH region or for at least 2 years since the discontinuation of clinical development of the IP. In addition, all subjects medical records and other source documentation will be kept for the maximum time permitted by the hospital, institution, or medical practice.

12. Statistical Considerations

Up to 30 patients will undergo a dynamic whole-body scan with ^{68}Ga -PSMA_{Gen} and later ^{68}Ga -PSMA_{cyc} with a maximum time of 2 days and a minimum time of 6 h between the two injections. All 22 patients will receive ^{68}Ga -PSMA_{Gen} at a specific activity of 1-2 Ci/ μmol , the typical specific activity used in clinical trials with ^{68}Ga -PSMA. We expect the ^{68}Ga -PSMA_{cyc} to be delivered and injected at a specific activity of 0.1- 2.0 Ci/ μmol given the rigors of delivery. We will accept doses in this range as the prior small animal imaging was designed to understand the affect of specific activity over a 20X range.

For a power of 80% a calculation of the sample size needed to test odds ratio (equality test) was performed. A sample size of 22 would give a power percentage of 18.47 with a type 1 error of 5%. This power percentage is sufficient in providing confidence that the findings will reflect a true effect. The median statistical power of studies in the neurosciences is between ~8% and ~31%. We will not and should not be focusing on p-values but rather the estimates of the effect size with its confidence intervals.

Estimating repeatabilities using a mixed effects model framework has proven to be powerful, the repeatability (r) is calculated as the variance among group means (group-level variance) over the sum of group-level and data-level (residual) variance (v). A Pearson's correlation coefficient will demonstrate also present the repeatability of results. Intraclass correlation values for both groups will be calculated to test if the groups differ in repeatability. These collection of tests(functions) for estimating repeatability of measurements with a single grouping factor are all performed in R statistical software.

To quantify the agreement between the two scans, we will use the repeated measures correlation coefficient to account for multiple observations per subject. We will calculate the repeated measures correlation-coefficient for the SUVmax and SUVmean for reference regions as well as regions suspicious for metastatic disease. We will measure SUVmean and SUVmax of the same Regions of Interest (ROI) in both scans using the PET analysis software we use in our clinical practice. The two scans will be retrieved and the exact same ROIs will be drawn at the same time for the two scans (software offers a copy-paste function so that no discrepancies exist between the two measurements). The SUVmean and SUVmax obtained from both scans for each Region of Interest will then be analyzed to determine the within-subject coefficient of variation value as measured by the Bland Altman analysis. If the agreement between the two scans lies within an acceptable rate (which we consider 30% based on previously published data), we will consider the two methods equivalent.

Also, as aforementioned the Bland-Altman Test presents proof of repeatability analysis.

13. Adverse Event Reporting Requirements

Adverse event (AE) monitoring and reporting is a routine part of every clinical trial. The investigator will be required to provide appropriate information concerning any findings that suggest significant hazards, contraindications, side effects, or precautions pertinent to the safe use of the drug or device under investigation. Safety will be monitored by evaluation of adverse events reported by subjects or observed by investigators or research staff, as well as by other investigations such as clinical laboratory tests, x-rays, electrocardiographs, etc.

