PI	Principal Investigator
REDCap	Research Electronic Data Capture
SAE	Serious Adverse Event
SUSAR	Suspected Unexpected Serious Adverse Reaction
UIRTSO	Unanticipated Problem Involving Risks to Subjects or Others
WCM	Weill Cornell Medicine
WCINYP	Weill Cornell Imaging NewYork Presbyterian
PCa	Prostate Adenocarcinoma
⁶⁸Ga	Gallium-68
PET	Positron Emission Tomography
ROI	Regions of Interest
PSMA	Prostate Specific Membrane Antigen
Ga-PSMAcyc	Ga-PSMA cyclotron
Ga-PSMAGen	Ga-PSMA generator

1. Protocol Summary

[figure not shown]
Full Title:	Evaluation of a ⁶⁸ Ga Small Molecule PSMA Antagonist Produced by two different Methods
Clinical Phase:	I/II
Principal Investigator:	[name]
Study Description:	Patients with metastatic prostate cancer will undergo two protocol ⁶⁸ Ga-PET scans within 24-48h with ⁶⁸ Ga-PSMA-cyclotron and ⁶⁸ Ga-PSMA-generator radiotracers. The goal of the study is to evaluate repeatability and equivalence across the different ⁶⁸ Ga-PSMA production methods.
Sample Size:	Up to 30 patients will be enrolled in the study as defined by protocol criteria.
Enrollment:	30 patients will be enrolled in this study
Study Population:	Patients with metastatic prostate adenocarcinoma
Enrollment Period:	2 years
Study Design:	Single-dose, non-randomized design. Patients with metastatic prostate adenocarcinoma will be administered a single intravenous dose of each of the study drugs ⁶⁸ Ga-PSMA-cyclotron and ⁶⁸ Ga-PSMA-generator 24-48 hours apart.
Description of Sites/ Facilities Enrolling	
Participants:	This is a single site study. All study procedures will be performed in the NYP/WCMC facilities, CBIC, and WCINYP.
Study Duration:	2 years
Participant Duration:	3 Visits: 1 screening/consent and 2-infusions imaging. The duration of patient participation can be up to 4 weeks, depending on eligibility, and the scheduling and completion of required study visits
Study Agent/Device Name	
Intervention Description:	⁶⁸ Ga-PSMA-cyclotron and ⁶⁸ Ga-PSMA-generator; single dose each, approximately 100-300 mBq.
Primary Objective:	
• To evaluate equivalence of two processes to create ⁶⁸Ga-HBED-PSMA (⁶⁸Ga-PSMA-cyclotron vs. ⁶⁸Ga-PSMA-generator)
Secondary Objectives:	
• Comparative dosimetry and biodistribution (⁶⁸Ga-PSMA-cyclotron vs. ⁶⁸Ga-PSMA-generator), whole body excretion/ metabolism in patients with confirmed metastatic PCa

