3.1 Overall Design

Thirty patients with metastatic prostate cancer that have undergone standard-of-care staging at WCMC will be considered for enrollment. For this study, enrolled patients will undergo a total of two whole-body dynamic ^{68}Ga -PET scan protocols of at least 0-75 min and at most 0-90 min scan time post injection, depending on the amount of injected dosage. A 6 to 48 hour gap will be introduced between the two scans. The first scan will occur after a baseline clinical evaluation, which will include a history, physical, and baseline lab draw. Blood work will be obtained before, during and after the scan. The radiotracers will be evaluated for repeatability and equivalence across the different production methods. This will include basic pharmacokinetics, distribution, metabolism and excretion.

Up to 30 patients will undergo each two whole-body dynamic scans, initially with ^{68}Ga -PSMAcyc and later with ^{68}Ga -PSMagen (with a minimum time of 6 h and maximum time of 2 days between the two injections). All patients will receive ^{68}Ga -PSMagen from the CBIC core and ^{68}Ga -PSMAcyc from NCM pharmaceuticals at a specific activity of 1-2 Ci/ μmol , the typical specific activity used in published clinical trials with ^{68}Ga -PSMA (10).

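### The sample size is given as 30, up to 30 and 22; the only power statement uses 22, and the 30% equivalence rule names no patient count, analysis set or time of analysis

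*Combined protocol and SAP*

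**What the plan says.** Three parts of the document give a patient number.

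- **Protocol Summary.** The sample size row reads "Up to 30 patients will be enrolled in the study as defined by protocol criteria". The enrolment row below it reads "30 patients will be enrolled in this study". The first is a ceiling and the second a fixed number.
- **Section 3.1, Overall Design.** "Thirty patients with metastatic prostate cancer that have undergone standard-of-care staging at WCMC will be considered for enrollment", and in the next paragraph "Up to 30 patients will undergo each two whole-body dynamic scans". Being considered for enrolment is not the same as being enrolled, and the second statement is again a ceiling.
- **Section 12, Statistical Considerations.** The first sentence begins "Up to 30 patients will undergo a dynamic whole-body scan with". The next says "All 22 patients will receive" the generator product at a given specific activity. The power paragraph then says "For a power of 80% a calculation of the sample size needed to test odds ratio (equality test) was performed", followed by "A sample size of 22 would give a power percentage of 18.47 with a type 1 error of 5" per cent.

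The end of Section 12 gives the primary rule: the two production methods are called equivalent if agreement between the scans is within 30%. That text, like the endpoint text in the Protocol Summary, analyses the SUV values from both scans for each region of interest. It gives no number of patients, no named analysis set and no time at which the rule is applied.

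**The concern.** A reader cannot tell how many patients the trial aims for. Taken alone, the word all in the Section 12 dosing sentence makes 22 the whole cohort, yet the sentence before it allows 30. The figure 22 could be the target, the expected number of complete pairs or a leftover from another version of the design. The document does not say. It gives no allowance for dropout, no evaluable number and no minimum.

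Two things depend on the answer. The power statement is tied to 22, so it does not describe a trial of 30. The primary verdict is a threshold on an estimate whose precision depends on the number of pairs, and that number is left open. Some loss of pairs is foreseeable: there are two imaging visits, each dynamic scan lasts 75 to 90 minutes, and Section 8.2 lets patients withdraw by declining a scan at any point. Without a defined analysis set, the handling of unpaired patients would be settled after the data are in.

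**Working it through.** **1. The counts side by side**

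| Place | Number | Nature |
|---|---|---|
| Protocol Summary, sample size | up to 30 | ceiling |
| Protocol Summary, enrolment | 30 | fixed |
| Section 3.1, first paragraph | 30 | considered for enrolment |
| Section 3.1, second paragraph | up to 30 | scanned twice |
| Section 12, first sentence | up to 30 | scanned |
| Section 12, second sentence | 22 | all patients dosed |
| Section 12, power | 22 | basis of 18.47% |
| Section 12, 30% rule | none | – |

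**2. The plan's own figure**

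The 18.47% cannot be reproduced. The document gives no odds ratio, event rate or sidedness, and does not say whether 22 is a total, a number per group or a number of pairs. Working backwards with 11 or 22 per group, one- or two-sided 5% and an assumed base rate of 0.1 to 0.5, the odds ratio that yields 18.47% runs from about 1.6 to 3.6. The figure can be neither confirmed nor refuted.

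**3. What 30 instead of 22 would do to that power**

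Use the normal approximation, power = Φ(δ√(n/22) − z), with δ chosen so that power is 0.1847 at n = 22. Then δ = Φ⁻¹(0.1847) + z = −0.898 + z, and √(30/22) = 1.168.

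- One-sided, z = 1.645: δ = 0.747; 0.747 × 1.168 = 0.873; Φ(0.873 − 1.645) = 22.0%.
- Two-sided, z = 1.960: δ = 1.062; 1.062 × 1.168 = 1.241; Φ(1.241 − 1.960) = 23.6%.

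Neither count comes near the 80% that the same paragraph names.

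**4. What 30 instead of 22 would do to the 30% rule**

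The following are my assumptions, not the document's: one normal paired difference per patient, no mean difference, and a pass if the estimated within-subject coefficient of variation (CV) is at most 30%. Then the probability of passing is P(χ²ₙ ≤ n(30/CV)²).

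| True CV | Limit at n = 22 | Pass at 22 | Limit at n = 30 | Pass at 30 |
|---|---|---|---|---|
| 30% | 22.00 | 54.0% | 30.00 | 53.4% |
| 32% | 19.34 | 37.6% | 26.37 | 34.4% |
| 34% | 17.13 | 24.4% | 23.36 | 20.0% |
| 36% | 15.28 | 15.0% | 20.83 | 10.7% |

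With one look at a fixed count, the choice of 22 or 30 moves the pass rate by about 3 to 4 points at a true CV of 32% to 36%, and by less than 1 point at 30%.

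**5. Illustration only: what an unfixed analysis time could permit**

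Suppose the rule were checked after each patient from 22 to 30 and the first pass counted. In 200,000 simulated trials under the same model, the pass rate would be 48.4% at a true CV of 32%, 32.5% at 34% and 20.4% at 36%. The protocol plans no such looks. These figures only show why the time of analysis should be written down.

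**The case against.** The strongest reply is that 22 is a stray figure and the analysis is clear enough without it. Much of this stands. The sentence containing 22 concerns specific activity, and the parallel sentence in Section 3.1 refers to all patients with no number. The endpoint text covers values from both scans and restricts nothing to 22. Enrolment is also bounded: the Protocol Summary gives a two-year enrolment period and a ceiling of 30, and Section 3.4 ties the end of the study to the last scheduled visit or procedure.

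Two stronger readings should therefore be set aside.

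- A reader might infer that 30 − 22 = 8 of 30 patients (27%) fall outside the primary analysis. The documents do not say so. No analysis set is defined for anyone, so no particular eight are excluded, and a sentence about all patients leaves no remainder.
- A reader might infer that the verdict may be taken at any count from 22 to 30. Nowhere is 22 a minimum or a stopping point, up to 30 has no floor, and no interim look or running estimate is described.

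The model in the working is also simpler than the planned data, which have several regions per patient and both SUVmax and SUVmean. Most of the risk of a false pass in that model comes from judging a point estimate without a confidence limit, which is a separate matter.

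The reply does not remove the contradiction. Consecutive sentences of the statistical section disagree on the number of patients, and the only power calculation uses the number that appears nowhere outside that section. An enrolment ceiling and an end-of-study definition do not fix the analysis set or the time at which the 30% rule is applied.

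**Conclusion.** The point holds as an internal inconsistency that should be corrected. The current text gives 30, up to 30 and 22 without reconciling them. The power statement rests on 22, and the primary rule has no stated count, analysis set or analysis time.

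The size is modest where it can be measured: about 3.5 points of power one-sided (18.47% to 22.0%), about 5.1 points two-sided (18.47% to 23.6%), and about 3 to 4 points in the pass rate at a single look for a true CV of 32% to 36%. The power comparison assumes a normal approximation scaled from the plan's own 18.47%. The pass rates assume one normal difference per patient, zero mean difference and a point-estimate rule. The inconsistency itself rests on the text alone and needs none of these assumptions.

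**What to change.** - State one enrolment number in the Protocol Summary, Section 3.1 and Section 12.
- Replace the 22 in the Section 12 dosing sentence to match, or have the sponsor say what 22 represents. It should not be relabelled as an expected number of evaluable pairs unless the sponsor confirms that this was meant.
- Restate the power or precision statement at the chosen number.
- Define the primary analysis set as every patient with both scans.
- State that the 30% rule is applied once, after the last enrolled patient's second scan.
- Report how many enrolled patients have no pair, and why.

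The cost is wording in three places and one recalculation, and the correction itself requires no additional patients. The small downside is that the sponsor gives up flexibility on the final count.

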2.4 Risk/Benefit Assessment

2.4.1 Known Potential Risks

Pharmacologic effects of HBED-PSMA

HBED-PSMA has been injected for PET imaging in more than 500 published patients. No drug related side effects have been observed. This is expected because the mass of compound is minimal, less than 10 micrograms.

Radiation exposure from PSMA PET/CT imaging

As part of this scan there is radiation delivered from the ^{68}Ga and from the low dose CT scan that are performed as part of the PET/CT for attenuation correction and co-registration. Although any exposure to ionizing radiation has the potential to cause some harm to tissue, the radiation exposures in this study are comparable to the low-level exposures associated with common diagnostic procedures such as CT scanning. There remains a low theoretical risk of developing cancer at some point later in life as a result of the radiation exposure received in this study. This risk is much smaller than the clinical risks posed by the patient's current cancer or the salvage radiation therapy the patient would be receiving. Participants should not father a baby while on this study. Acceptable birth control methods include abstinence, double barrier method, surgically sterilized patient or partner. Radiation exposure due to injection of $^{68}\text{Ga-HBED-PSMA}$ and CT imaging is provided in table 1.

Table 1: ⁶⁸Ga-PSMA 11 Patient Dosimetry (per session)

			Dose per CT Scan rad	# of Injections/CT scans
Activity of 68Ga-PSMA 11 (maximum)	3.3	mCi	0.90	1
Low dose WB CT scan	80	mA	0.90	1
Ultra-low dose WB CT scan	10	mA	0.11	3
			Total CT dose:	1.01

Target Organ	Absorbed Doses			
	rad/mCi	rad/ admininstration	rad for 4 CT scans	Total rad
Adrenals	0.0525	0.173	1.23	1.40
Brain	0.0333	0.110	1.23	1.34
Breasts	0.0326	0.107	1.23	1.34
Gallbladder Wall	0.0533	0.176	1.23	1.41
LLI Wall	0.0455	0.150	1.23	1.38
Small Intestine	0.0603	0.199	1.23	1.43
Stomach Wall	0.0444	0.147	1.23	1.38
ULI Wall	0.200	0.66	1.23	1.89
Heart Wall	0.0403	0.133	1.23	1.36
Kidneys	0.969	3.20	1.23	4.43
Liver	0.114	0.377	1.23	1.61
Lungs	0.0377	0.125	1.23	1.35
Muscle	0.0389	0.128	1.23	1.36
Pancreas	0.0511	0.168	1.23	1.40
Red Marrow	0.0340	0.112	1.23	1.34
Osteogenic Cells	0.0525	0.173	1.23	1.40
Skin	0.327	1.08	1.23	2.31
Spleen	0.165	0.54	1.23	1.77
Testes	0.0385	0.127	1.23	1.36
Thymus	0.0366	0.121	1.23	1.35
Thyroid	0.0359	0.118	1.23	1.35
Urinary Bladder Wall	0.481	1.59	1.23	2.82
Total Body	0.0459	0.151	1.23	1.38
Effective Dose (rem)	0.0873	0.288	1.23	1.52

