2.5.2.2 Small animal ^{68}Ga -HBED-CC and repeatability

Several experiments were performed in mice to determine repeatability of the ^{68}Ga -HBED-CC which are published at Molecular Imaging and Biology with the following figures representing a synopsis of the results.

Representative PET images of mice bearing PC3-PIP xenografts imaged with ^{68}Ga -HBED-PSMA on three consecutive days

Normalized uptake values in mice bearing PC3-PIP tumor xenografts that were imaged using ^{68}Ga -HBED-PSMA either consecutively for three days (Group 2, mice 4, 5, and 6) or alternative days with ^{68}Ga -HBED-PSMA and administered with ^{68}Ga -HBED-PSMA on day 2 (Group 1, mice 1, 2, and 3) one hour post-administration of tracer.

3. Study Design

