3.3 Justification for Dose

Patients will be injected with 100-300 MBq of ^{68}Ga -HBED-PSMA (from either the generator or cyclotron source) via a catheter. ^{68}Ga -PSMA PET/CT will be acquired using a Siemens Biograph mCT™ PET/CT scanner. Please see details in section 7.1.

The goal is to administer this amount of the imaging probe labeled with 2.5 MBq of ^{68}Ga per kg body weight with a minimum of 100 MBq and maximum of 300 MBq ^{68}Ga per patient.

The whole-body dynamic ^{68}Ga -PSMA scans will involve an initial dynamic scan at a pelvic scanner bed position centered over the prostate tissues for the first 10min post injection (p.i.), followed by multiple successive whole-body scans (passes) at least 10-75 min and at most 10-90 min post injection, depending on the amount of injected dosage. A fixed scan time of 30sec per bed position per pass will be used with an adjustable total number of passes. The PET data collected from at least the last six passes will be summed at each bed position and combined over all bed positions to produce whole-body static ^{68}Ga -PSMA images equivalent of a total acquisition time of $6 \times 30 \text{ sec} = 180\text{sec}$ or 3 min/bed position from all summed passes.

Due to the short physical half-life of ^{68}Ga and the decreasing elution efficiency of the $^{68}\text{Ge}/^{68}\text{Ga}$ generator during its lifetime, the amount of radioactivity injected per patient will necessarily vary. If the amount of activity per kg body weight differs by more than 25% from the recommended dose of 2.5MBq/kg of body weight, the effective total acquisition time per bed position from all passes will be adjusted by increasing the total number of passes, in increments of one pass, while keeping fixed the scan time per bed per pass. The adjustment of the total number of passes will result in the respective adjustment of the total scan time up to 90 min post injection. The total number of passes will be adjusted such that the product of total acquisition time per bed position from all summed passes participating in the synthesis of the equivalent static PET images and of the injected activity is at least 7.5 MBq/kg*min or the total scan time reached 90 min.

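### Section 12 allows the cyclotron product a 20-fold specific-activity range against 2-fold for the generator product, and no analysis separates ligand amount from production route

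*Combined protocol and SAP*

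**What the plan says.** Section 12 gives the generator product "at a specific activity of 1-2 Ci"/µmol. It expects the cyclotron product "to be delivered and injected at a specific activity of 0.1- 2.0 Ci"/µmol, "given the rigors of delivery". The support offered is the animal work: "We will accept doses in this range as the prior small animal imaging was designed to understand the affect of specific activity", said to span 20-fold.

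Three other places bear on this.

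- Section 3.1 supplies the generator product from the core facility and the cyclotron product "from NCM pharmaceuticals at a specific activity of 1-2 Ci"/µmol, which reads as one range for both.
- Section 2.5.2.2, the only section on animal imaging, opens: "Several experiments were performed in mice to determine repeatability of the" tracer. Its text names six mice in two groups and does not mention specific activity. The figures that carry the results are not in the text available.
- Section 2.4.1 explains the absence of drug-related side effects in published patients by ligand mass: "This is expected because the mass of compound is minimal, less than 10 micrograms".

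The analyses in section 12 are mixed-model repeatability, Pearson correlation, intraclass correlation, repeated-measures correlation, and a Bland-Altman within-subject coefficient of variation (wCV). The methods are called equivalent if agreement is within 30%. None of these has specific activity or ligand amount as a covariate, stratum or sensitivity analysis.

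**The concern.** At a given injected activity, specific activity fixes how much ligand goes in. The wide range belongs to one product only, so differences in ligand amount run along the comparison under test. If uptake depends on ligand amount, that dependence enters the cyclotron/generator SUV ratio, and nothing planned can take it out again.

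The conclusion could then mislead in two ways. A real shift in uptake could be absorbed by the 30% limit and reported as equivalence. Or most cyclotron doses could arrive at high specific activity, and equivalence would be claimed for a range that was hardly sampled.

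The plan itself treats specific activity as relevant, since it sets ranges and argues for the wide one. The argument refers to what the animal work was designed to do and gives no result.

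**Working it through.** **1. The plan's own figure.** 2.0/0.1 = 20-fold (cyclotron), as stated; 2/1 = 2-fold (generator). Within one patient at equal activity, the cyclotron injection can carry from 1/2 = 0.5 times to 2/0.1 = 20 times the generator injection's ligand.

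**2. Ligand amount.** Amount (nmol) = (MBq/37)/(Ci/µmol). Section 3.3 sets 2.5 MBq/kg "with a minimum of 100 MBq and maximum of 300 MBq". The 175 MBq row assumes a 70 kg patient.

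| Activity | at 2 Ci/µmol | at 1 Ci/µmol | at 0.1 Ci/µmol |
|---|---|---|---|
| 100 MBq | 1.4 nmol | 2.7 nmol | 27 nmol |
| 175 MBq | 2.4 nmol | 4.7 nmol | 47 nmol |
| 300 MBq | 4.1 nmol | 8.1 nmol | 81 nmol |

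**3. Against the mass in section 2.4.1.** At 0.1 Ci/µmol even 100 MBq carries 27.03 nmol, which exceeds 10 µg for any ligand heavier than 10,000/27.03 = 370 g/mol. The molecular weight is not in the documents. For an assumed 800-1100 g/mol, 0.1 Ci/µmol gives about 22-89 µg over 100-300 MBq, and 1-2 Ci/µmol gives about 1-9 µg.

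**4. What a ligand effect would do.** Assumptions, none from the documents:

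- uptake proportional to 1/(1 + amount/M50), where M50 is the amount at which uptake halves;
- 175 MBq for both scans and 30 pairs;
- SD of the ln SUV ratio 0.25;
- specific activity log-uniform over each product's range;
- no true production effect.

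The worst-pair ratio is (1 + 2.36/M50)/(1 + 47.3/M50). wCV is taken on the log scale as the square root of (mean squared ln ratio)/2. The other columns are by simulation.

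| M50 (nmol) | Worst-pair ratio | Mean ratio | Mean wCV | Chance wCV > 30% | Power for slope (two-sided 5%) |
|---|---|---|---|---|---|
| 50 | 0.54 | 0.83 | 25% | about 6% | 91% |
| 100 | 0.69 | 0.90 | 20% | near 0 | 50% |
| 200 | 0.82 | 0.95 | 18% | near 0 | about 19% |
| 500 | 0.92 | 0.98 | 18% | near 0 | about 7% |

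**5. Why the limit absorbs a shift.** With baseline wCV w and a constant ln shift μ, wCV² = w² + μ²/2. At w = 10%, the limit is reached when μ = √(2(0.09 − 0.01)) = 0.40, a fall of 33%. At w = 25%, μ = √(2(0.09 − 0.0625)) = 0.235, a fall of 21%.

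**6. Precision of an equal-ligand estimate.** In the same simulation the slope on ln(amount ratio) has a standard error of about 0.05. The ln ratio at equal ligand amount has a standard error of about 0.076, against about 0.05 unadjusted: 0.076/0.05 ≈ 1.5.

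**The case against.** **Specific activity may be part of the product.** The objective concerns two processes for making the tracer, and section 12 ties the wide range to delivery. A lower SUV from a low-specific-activity dose would then be a real difference between products as delivered. This stands, and it is why the as-delivered comparison should remain primary. The plan does not say which comparison it intends, so a second estimate is still informative.

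**The animal evidence may exist.** The mouse work is cited as published and its figures are missing here. A reader might infer that specific activity was never studied in animals. The documents do not support that; they show only that the surviving text gives no results by specific activity.

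**False failure is unlikely.** A reader might infer that patients given low-specific-activity doses would fail the 30% limit and sink the trial. The limit applies to a study-level wCV, not to single pairs, and the simulated chance of exceeding it is small. The ratios of 0.54-0.92 are worst pairs, not averages.

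**Detection is not assured.** A reader might expect 30 pairs to reveal any important ligand effect. At M50 100 nmol the slope would be missed half the time.

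**No effect in patients is shown.** This is correct, and every consequence here is conditional on one. The mass conflict with section 2.4.1 is likewise an inconsistency to resolve, not evidence of harm.

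**The point may lapse.** If sections 3.1 and 12 are reconciled to the same range for both products, most of it does. It remains if the section 12 ranges stand.

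**Conclusion.** The gap holds in a limited form. The text shows an asymmetric specific-activity range, a conflict with section 3.1, a lower limit hard to square with the ligand mass in section 2.4.1, and no analysis that uses specific activity. While the section 12 range stands, a ligand-amount effect and a production-route effect cannot be told apart.

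The size is unknown because M50 is not given. Over the assumed M50 of 50-500 nmol, the mean SUV ratio would be biased by 2% to 17% (1 − 0.98 to 1 − 0.83) with no production effect. The 30% criterion would be met in about 94% of trials at M50 50 and in nearly all at 100 or more. These figures also rest on the assumed SD, activity and spread of specific activity; doses clustered near 0.1 Ci/µmol would give a larger bias. The main risk is therefore a bias that passes unnoticed or an equivalence claim wider than the data, rather than a wrongly failed trial. It is an inexpensive improvement and does not invalidate the primary comparison.

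**What to change.** 1. Reconcile the specific-activity ranges in sections 3.1 and 12, and the 0.1 Ci/µmol lower limit with the ligand mass in section 2.4.1. No view is taken here on which is right.
2. State that the as-delivered comparison is primary.
3. Name specific activity at injection and ligand amount as recorded fields for both products. Section 7.1 promises only a log of doses, and a certificate of analysis is stated only for the generator route (2.5.1), so the cyclotron values cannot be assumed to be on file.
4. Prespecify a sensitivity analysis: regress each patient's ln(SUV cyclotron/SUV generator) on ln(ligand amount cyclotron/generator). Report the ratio at equal ligand amount with its 90% CI beside the unadjusted ratio.
5. Limit the equivalence statement to the specific-activity range actually injected, and report that range for each product.
6. If the animal work is to justify the range, cite its results by specific activity.

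The cost is SAP wording, one regression and two fields per injection. The equal-ligand estimate is about 1.5 times less precise than the unadjusted one and assumes a log-linear relation. Power for the slope is about 50% at M50 100 nmol and under 20% at 200 or more, so the SAP should say that a null slope is not evidence of no effect.
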